| | 2. At least two (>4 weeks interval) basal FSH≥15IU/L, with or without oligomenorrhea or |
| | menopause. |
| | 3. Informed consent, voluntary experiment. |
| | Exclusion criteria: |
| | 1. pregnant and lactating patients; |
| | 2. Patients with endometriosis , adenomyosis , endometrial lesions (submucosal fibroids , |
| | endometrial polyps, etc.), uterine fibroids >4cm or hysterectomy; |
| | 3. Patients with known or suspected history of breast cancer and estrogen-dependent |
| | malignancies; |
| | 4. a personal history of venous thromboembolism (VTE) or with a high risk of VTE (including |
| | body mass index > 30 kg/m ² , smoking, family history of thrombophilia); |
| | 5. Porphyria patients; |
| | 6. Patients with serious primary diseases such as cardiovascular, liver, kidney, hematopoietic |
| | system or mental illness; |

- 7. Patients who are participating in other clinical trials or have participated in other clinical trials within the past three months;
- 8. Patients with suspected or real history of alcohol and drug abuse;
- 9. Known allergy to the investigational drug or its components;
- 10. Other patients deemed unsuitable for participation in this trial by the investigator.

Note: Patients who were receiving hormone replacement therapy at the time of recruitment were required to take at least a 3 -month suspension of medication to participate in this trial.

Trial grouping

and medication

1 POI patient

According to the random sequence generated by computer, eligible patients were randomly assigned to Kuntai group, control group and combination group according to 1:1:1.

- (A) Kuntai group (30 cases): Oral Kuntai capsules, 4 capsules at a time, 3 times a day, 28 days as a course of treatment, taking medicine for 3 courses;
- (B) Control group (30 cases): the sequential regimen of estrogen and progesterone was used, and the drug was estradiol tablets/estradiol dydrogesterone tablets (fenmetone), and red tablets (estradiol, 2 mg/d), and gray tablets (estradiol, 2 mg/d, dydrogesterone, 10 mg/d) were taken for the next 14 days, 28 days as a course of treatment, and three courses of medication were taken.
- (C) Combination group (30 cases): On the basis of hormone therapy, Kuntai Capsules were added, and the dose was the same as that of Kuntai group and hormone group for 3 months.

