- 2. Patients with POI in subclinical stage: self-control before and after experiment group (30 cases): Oral Kuntai capsules, 4 capsules at a time, 3 times a day, 28 days as a course of treatment, taking medicine for 3 courses of treatment.

Treatment and

follow-up

- 1. Course of treatment: 28 days as a course of treatment, taking medicine for 3 courses of treatment
- 2. Visit points: before treatment (stage V $_{0}$, screening period, days -35 $\rm to~0$), baseline period (day
- 0), after 3 months of treatment (stage V_1 , days 84 to 105), drug withdrawal 3 months later (V_2 stage, 168-210 days) and 6 months after drug withdrawal (V_3 stage, 252-315 days).

Specific inspection items include:

- 1. The patient 's hormone levels (basal FSH, LH, E₂) were detected in V₀, V₁, and V₂ stages;
- 2 Anti-Müllerian hormone (AMH) was detected in patients at V 0 and V 1 stages;
- 3 The patients underwent B-ultrasound at V 0 and V 1 stage to monitor the follicular development,

| | record the number of antral follicles (AFC), ovarian hemodynamic parameters (PSV, EDV, S/D, RI |
|----------------|---|
| | and PI); |
| | 4. Modified Kupperman score was performed in V $_{0}$, V $_{1}$ and V $_{2}$ stage; |
| | 5 Pregnancy was recorded at the V $_2$ outpatient follow-up for patients with reproductive needs; |
| | 6 patients at V $_{0}$ and V $_{1}$ to detect blood routine (RBC, WBC, PLT, HGB) , liver function (ALT, |
| | AST) and renal function (BUN, Cr), and recorded adverse events. |
| | |
| | Note: |
| | 1 Basal follicle-stimulating hormone (FSH) \geq 15IU/L at first visit in patient V0, and if other |
| | inclusion criteria are met, if the patient has a history of testing with a baseline FSH ≥ 15 IU/L in |
| | the past (interval> 4 weeks), he or she can be included in this study and drug therapy can be |
| | started; (Interval > 4 weeks) If the basic FSH \geq 15 IU/L has not been diagnosed, the patient is |
| | required to visit the hospital again after 4 weeks. If the basic FSH is still \geq 15 IU/L, they can be |
| | included in this study and drug therapy can be started. |
| | 2 For patients with regular menstrual periods, the basal FSH and antral follicle count (AFC) |
| | should be followed up on the 2nd to 4th day of the menstrual cycle. If the patient has menstrual |
| | cramps after the follow-up and has not exceeded the visit window, they are required to re-examine |
| | on the 2nd to 4th day of the menstrual cycle and record the examination data. |

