| study endpoint | Primary endpoint : FSH, modified Kupperman score |
| | Secondary endpoints : |
| | (1) FSH/LH, LH, E ₂ ; (2) Antral follicle count (AFC); (3) Anti- Müllerian hormone (AMH); (4) |
| | Proportion of patients with normal menstruation; (5) Ovarian hemodynamics parameters (PSV, |
| | EDV, S/D, RI and PI); (6) Clinical pregnancy rate (patients with reproductive needs). |
| security | 1 Blood routine (RBC, WBC, PLT, HGB), liver function (ALT, AST) and renal function (BUN, |
| indicators | Cr); |
| | 2 Patient adverse events were recorded. |

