A Multi-center Clinical Study on the Efficacy and Safety of Kuntai Capsule Alone and in Combination With Hormones in the Treatment of Early-onset Hypoovarian Function

NCT05021094

Date : August 4 , 2021

Statistical analysis

The case observation form completed by the test center was reviewed and returned by the project team of Shanghai Haitian Pharmaceutical Technology Development Co., Ltd., and the data was processed by a statistical analyst. The data in the case report form is entered in two copies, and the database is locked after verification and confirmation. SPSS26.0 software was used for statistical analysis. The full analysis set (FAS) and the per-protocol set (PPS) were used for effectiveness analysis, and the safety data set (SS) was used for safety analysis. Measurement data were expressed as mean \pm standard deviation ($\bar{x} \pm s$), multiple time points were compared by repeated measures analysis of variance, and pairwise comparisons were by Bonferroni test; enumeration data were expressed by the number of cases or percentages, and χ^2 was used.Test for statistical comparison.P<0.05 indicated that the difference was statistically significant.

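### Two primary endpoints are each tested at P<0.05 with no success rule, no adjustment across them and an undefined Bonferroni family, so the error rate of the efficacy conclusion is not fixed

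*SAP*

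**What the plan says.** The study endpoint entry of the protocol's Research Proposal Summary reads "Primary endpoint : FSH, modified Kupperman score". It does not rank the two endpoints or say how they combine.

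Under trial grouping and medication, "eligible patients were randomly assigned to Kuntai group, control group and combination group according to 1:1:1", with 30 cases planned in each arm. The comparator is active: "Control group (30 cases): the sequential regimen of estrogen and progesterone was used". The stated purpose covers Kuntai both alone and added to hormones, so at least two contrasts with control are of interest. A fourth group is not randomised ("self-control before and after experiment group (30 cases") and is left out of the figures below.

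The inspection items under treatment and follow-up place both endpoints at V0, V1 and V2 ("Modified Kupperman score was performed in V" 0, 1 and 2, and FSH likewise). No visit is named as primary.

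The SAP's statistical analysis section is a single paragraph. For measurement data, "multiple time points were compared by repeated measures analysis of variance, and pairwise comparisons were by Bonferroni test". For efficacy, "The full analysis set (FAS) and the per-protocol set (PPS) were used for effectiveness analysis". The decision rule is "P<0.05 indicated that the difference was statistically significant". No rule links the two endpoints.

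**The concern.** A Bonferroni step within one outcome, whether over arms or over visits, does nothing about having two outcomes. If a positive result on either FSH or Kupperman would be reported as efficacy, the trial has two chances to succeed and 5% describes each test, not the conclusion.

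The scope of the Bonferroni step matters as much. It appears in the sentence on multiple time points. It may cover the three arm pairs, or only comparisons between visits, which would leave the arm contrasts unadjusted.

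Because neither the success rule nor the family is written down, the reading could be chosen after the results are known. The error rate actually run could then lie below 5% or well above it.

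**Working it through.** **The plan's own figure.** The only derived number in the documents is enrolment: 120 / (1 - 0.20) = 150, which reproduces. No power, effect size or SD is given, so the 30 per group cannot be checked.

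**Inputs from the documents.** Two primary endpoints; threshold 0.05; three randomised arms (three pairs, two of them against control); 30 per arm.

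**Assumptions.** Two-sided tests (sidedness is not stated); normal data; pooled variance on 3 × (30 - 1) = 87 degrees of freedom; one visit and one analysis set; randomised arms only; correlation between FSH and Kupperman from 0 to 0.7. The one-visit comparison approximates the planned repeated-measures analysis. A group-by-time ANOVA gave similar figures (8.4-9.8%).

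**Either endpoint sufficient, no true difference anywhere.** With independent endpoints, error = 1 - (1 - e)², where e is the error within one endpoint:
- one omnibus test at 0.05: 1 - 0.95² = 9.75%;
- combination versus control alone at 0.05/3: 1 - (1 - 0.0167)² = 3.3%;
- two contrasts with control at 0.05/3, e = 3.1% by simulation because they share the control arm: about 6.1%;
- the same two contrasts at 0.05, e = 9.1%: about 17%.

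Simulation (400,000 trials per correlation for most rows; 60,000 for combination versus control alone) shows how far correlation lowers these:

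| Tests on each endpoint | Correlation 0 | Correlation 0.7 |
|---|---|---|
| One omnibus three-arm test at 0.05 | 9.7% | 8.4% |
| All three pairs at 0.05/3 | 8.5% | 7.4% |
| Two contrasts with control at 0.05/3 | 6.1% | 5.4% |
| Two contrasts with control at 0.05/2 | 9.0% | 7.8% |
| Two contrasts with control at 0.05 (Bonferroni over time points only) | 17.2% | 14.8% |
| Combination versus control alone at 0.05/3 | 3.3% | 2.8% |

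**Both endpoints required.** The worst case is one endpoint with an effect so large that it always succeeds and the other with none. The error is then e for the null endpoint:
- one test at 0.05: 5%;
- two contrasts unadjusted: about 9%;
- three contrasts unadjusted: about 12%;
- two contrasts at 0.05/3: about 3%;
- two contrasts at 0.025: about 4.6%.

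So requiring both keeps 5% only with one test per endpoint or adjusted arm contrasts.

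**After the repair, either endpoint sufficient (correlation 0 to 0.7).** Omnibus tests at 0.025 each give 4.9% to 4.3%. Four tests at 0.0125 (two endpoints by two contrasts) give about 4.6% to 4.1%.

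**The case against.** The strongest reply is that the documents never say that either endpoint is enough. If the sponsor means both to be required and adjusts the arm contrasts, there is no inflation. Some either-endpoint readings also sit below 5%: combination versus control alone at 0.05/3 (about 3%), or pairwise tests run only after a significant group-by-time interaction over V0, V1 and V2 (about 4-4.5% on V1 change scores, 1-2% on V1 values). At an endpoint correlation of 0.9 even the two contrasts at 0.05/3 fall to 4.5%. All of this stands. It is why the point concerns an unfixed error rate and not a demonstrated excess.

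It can also be said that a repeated-measures ANOVA may act as one global test over visits, so the absence of a primary visit is partly answered. That is fair, but the SAP does not name the effect to be tested, and a global test still leaves two endpoints.

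That this is a post-marketing re-evaluation described in a summary bears on how much detail to expect. It remains a randomised controlled trial with named primary endpoints and a significance threshold.

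A reader might infer more: that the plan runs at 10% or 17% error, or that V1 and V2, or the full analysis and per-protocol sets, are extra chances to win. The documents do not support this. They state no either-endpoint rule and do not say that any one visit or analysis set can carry the claim alone, so those routes are not counted.

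**Conclusion.** The gap is real and can be read directly from the two documents: two primary endpoints, one threshold, no rule joining them, and a Bonferroni step whose family is undefined.

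No single percentage describes the plan. With either endpoint sufficient, the readings tabulated above run from about 3% to 17%. The plainest of them, one omnibus test per endpoint, gives 8.4-9.7%. For the two control contrasts at 0.05/3 the excess over 5% is at most about one point; the larger problem arises if the arm contrasts are not adjusted at all. Nor is requiring both endpoints a complete answer: it fails (about 9% or 12%) when two or three arm contrasts go unadjusted.

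These sizes rest on the assumed correlation, on normal data and on a one-visit comparison at 30 per arm. The conclusion that the error rate is undetermined rests on the text alone. It should be corrected, and the correction is short.

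**What to change.** Before comparative data are seen, add to the SAP and to the protocol's endpoint entry:

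1. One success rule: either Holm (or 0.025 each) across FSH and Kupperman, or both required at 0.05.
2. The adjusted family, stated to include the primary arm contrasts. If either endpoint suffices and both contrasts with control are primary, that is four tests. If both endpoints are required, keep a Bonferroni or Holm adjustment over the two contrasts.
3. The visit and the contrasts to which the rule applies.

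This takes a few sentences and no extra patients or assessments, though the sponsor must first decide what counts as success.

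The price is power. For a two-sample t test at 80% power with 30 per arm, the detectable difference is 0.74 SD at 0.05, 0.81 SD at 0.025 and 0.89 SD at 0.0125. At the 0.74 SD effect, power per test falls from 80% to 71% and 61%. Requiring both endpoints at 0.05 gives joint power of 0.8 × 0.8 = 64% if they are independent and about 71% at correlation 0.7, when each has 80%; adjusting two contrasts as well would lower this further. Holm loses no more than the fixed split.
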